8.3.3 Primary Efficacy Analysis

The distribution of RFS will be estimated for each study arm using Kaplan-Meier methodology and compared between the two study arms using the log-rank test, stratified

by age ($< 60, \ge 60$ years) and relapse risk (poor risk cytogenetic or MRD-positive ($\ge 10^{-3}$), others). The hazard ratio and corresponding 95% CI will be estimated using the Cox proportional hazards model, stratified by age ($< 60, \ge 60$ years) and relapse risk (poor risk cytogenetic or MRD-positive ($\ge 10^{-3}$), others).

8.3.4 Additional Analyses of the Primary Efficacy Endpoint(s)

The following sensitivity analyses of RFS will be performed:

- Stratified log-rank test and stratified Cox proportional hazards model based on RFS data from investigator assessment.
- Stratified Wilcoxon test, Un-stratified log-rank test, and the Cox proportional hazards model for RFS testing.
- Stratified log-rank test and covariate-adjusted proportional hazards Cox model will include potential prognostic factors not used in the randomization stratification.
- Modified primary RFS definition with censoring subjects who received other non-protocol treatment for AML prior to relapse.

[figure not shown]
8.4 Secondary Efficacy Analyses

8.4.1 Key Secondary Efficacy Analyses

The key secondary endpoints include overall survival (OS), time to deterioration in GHS/QoL, PROMIS Cancer Fatigue SF 7a and MRD conversion rate. All subjects in the ITT population will be included in the secondary efficacy analyses.

Overall Survival (OS)

Overall survival is defined as the time from randomization to death from any cause. All events of death that occur prior to the cutoff date will be included in the analysis of OS. All subjects in the ITT population will be included in the analysis of OS.

[figure not shown]
Subjects who have not died will be censored at the last known alive date on or before the cutoff date. The last known alive date will be determined by selecting the last available date of the following study procedures: start date of adverse event, bone marrow collection, disease assessment, vital signs assessment, clinical laboratory collection, study drug administration, start date of concomitant medicine, survival follow-up, biospecimen sample collection, quality of life assessments, and performance status.

The distribution of endpoint OS will be estimated for each study arm using Kaplan-Meier methodology and compared between the two study arms using the log-rank test, stratified by age ($< 60, \ge 60$ years) and relapse risk (poor risk cytogenetic or MRD-positive ($\ge 10^{-3}$), others). The hazard ratio and corresponding 95% CI between the two study arms will be estimated using the Cox proportional hazards model, stratified by age (< 60, ≥ 60 years) and relapse risk (poor risk cytogenetic or MRD-positive ($\ge 10^{-3}$), others).

Time to Deterioration in GHS/QoL

The EORTC-QLQ-C30 is a 30-item patient-reported questionnaire composed of both multi item and single scales including 5 functional scales (physical, role, emotional, social, and cognitive), 3 symptom scales (fatigue, nausea and vomiting, and pain), a global health status/QoL scale, and 6 single items (dyspnea, insomnia, appetite loss, constipation, diarrhea, and financial difficulties). Subjects rate items on a 4-point scale ranging from 1 to 4 (1 = Not at All, 2 = A Little, 3 = Quite a Bit, and 4 = Very Much). The EORTC-QLQ-C30 was developed and validated for use in a cancer patient population, and its reliability and validity are highly consistent across different language-cultural groups. A change of 5 to 10 points is considered a small change and the lower bound (5) will be used to define the minimum important difference. A change of \geq 10 to \leq 20 points is considered a moderate change.

Time to deterioration in GHS/QoL is defined as the time from randomization to death from any cause or the first-time deterioration of ≥ 5 points in GHS/QoL score as measured by EORTC QLQ-C30. All subjects in the ITT population will be included in the analysis.

Subjects without any of the specified events will be censored at the date of the last GHS/QoL assessment. Subjects without any GHS/QoL assessment after the randomization will be censored at the date of randomization.

The distribution of endpoint time to deterioration in GHS/QoL will be estimated for each study arm using Kaplan-Meier methodology and compared between the two study arms using the log-rank test, stratified by age ($< 60, \ge 60$ years) and relapse risk (poor risk cytogenetic or MRD-positive ($\ge 10^{-3}$), others). The hazard ratio and corresponding 95% CI between the two study arms will be estimated using the Cox proportional hazards model, stratified by age ($< 60, \ge 60$ years) and relapse risk (poor risk cytogenetic or MRD-positive ($\ge 10^{-3}$), others).

PROMIS Cancer Fatigue SF 7a

PROMIS is a system of highly reliable, precise measures of patient-reported health status for physical, mental, and social well-being. PROMIS instruments measure concepts such as pain, fatigue, physical function, depression, anxiety and social function. Fatigue will be assessed using the PROMIS Fatigue SF that has been developed for use in oncology populations. PROMIS Fatigue SF 7a is a 7-item questionnaire that assesses the impact and experience of fatigue over the past 7 days. All questions employ the following five response options: 1 = Never, 2 = Rarely, 3 = Sometimes, 4 = Often, and 5 = Always. For Question 7, scores will be reversed. The recommended minimum important difference range is 3 to 5 points.

Patient reported outcome on fatigue will be assessed using the global fatigue score as measured by PROMIS Cancer Fatigue SF 7a. Scores will be computed according to the PROMIS Cancer Fatigue SF 7a scoring manual.

A linear mixed effects regression model with an appropriate covariance structure will be used to fit the longitudinal data. In the linear mixed effects regression model, stratification factors age ($< 60, \ge 60$ years) and relapse risk (poor risk cytogenetic or MRD-positive ($\ge 10^{-3}$), others), will be included as fixed factors. The model will also

include time, study arm, and study arm by time interaction. The following covariance structures will be explored: Unstructured (TYPE = UN), compound symmetry (TYPE = CS) and first-order autoregressive (TYPE = AR(1)). The covariance structure resulting in model convergence and the lowest Bayesian Information Criterion (BIC) will be used for analysis. Change from baseline scores from all post-baseline visits described in Appendix B will be compared between the two study arms based on the linear mixed effects model. Subjects without baseline score or any post-baseline score will be excluded from the linear mixed effects regression analysis.

MRD Conversion Rate

MRD conversion rate is defined as percentage of subjects with MRD $\geq 10^{-3}$ at randomization who convert to MRD $< 10^{-3}$ after initiation of therapy. Subjects whose MRD is $< 10^{-3}$ or missing at randomization will be excluded from the analysis. Subjects who are deemed MRD positive at baseline but do not have any post-baseline MRD result will be included in the analysis as non-conversion events.

[figure not shown]
The MRD conversion rates between the two study arms will be compared using Miettinen-Nurminen method stratified by age group ($< 60, \ge 60$ years). The difference and corresponding 95% CI in MRD conversion rate between the two study arms will also be provided using Miettinen-Nurminen method stratified by age group ($< 60, \ge 60$ years). In addition, the 95% confidence interval of MRD conversion rate in each study arm will also be provided using the binomial distribution (Clopper-Pearson exact method).

8.4.2 Supportive Secondary Efficacy Analyses

OS will be analyzed using all data collected in the extracted database. The same analysis method described in Section 8.4.1 will be applied.

8.5 Additional Efficacy Analyses

All subjects in the ITT population will be included in the additional efficacy analyses.

EORTC QLQ-C30

Exploratory analyses will be performed on the subscales/items from the EORTC QLQ-C30. Scores will be calculated as per the scoring manuals. Linear mixed effects regression models similar to that described for the analysis of PROMIS Cancer Fatigue SF 7a in Section 8.4.1 will be used to compare between the two study arms. Subjects without baseline score or any post-baseline score will be excluded from the linear mixed effects regression analysis.

[figure not shown]
EQ-5D-5L

The EQ-5D-5L is a generic preference instrument that has been validated in numerous populations. ^{6,7} The EQ-5D-5L has 5 dimensions: mobility, self-care, usual activities, pain/discomfort and anxiety/depression. These dimensions are measured on a 5-point scale: no problems, slight problems, moderate problems, severe problems, and extreme problems. The scores for the 5 dimensions are used to compute a single utility index score ranging from zero to 1 representing the general health status of the individual. The EQ-5D-5L status will be converted into a single preference-weighted health utility index score by applying country-specific weights (if available) or US weights (if not available). The EQ-5D-5L also contains a visual analog scale (VAS) to assess the subject's overall health. The minimum important difference for the EQ-5D-5L utility index score in cancer patients is 0.08, and the minimum important difference for EQ-5D-5L VAS is 7.⁷

Exploratory analyses will be performed on EQ-5D-5L. Scores will be calculated as per the scoring manuals. Linear mixed effects regression models similar to that described for the analysis of PROMIS Cancer Fatigue SF 7a in Section 8.4.1 will be used to compare between the two study arms. Subjects without baseline score or any post-baseline score will be excluded from the linear mixed effects regression analysis.

Health Care Resource Utilization

Number and percentage of subjects admitted to hospital during evaluation period will be summarized and compared between the two study arms using Fisher's exact test.

Percent of hospitalization stay over evaluation period will be summarized and compared between the two study arms using ANOVA model. The percent of hospitalization stay is defined as total duration of hospitalization divided by duration of evaluation period for each subject. In addition, reasons for hospital admission and treatment setting (e.g., inpatient unit, special care unit, etc.) will also be summarized.

The evaluation period is from the date of the first dose of study drug or date of randomization (randomized but not received study drug) to 30 days of the end of Cycle 24, disease relapse, study discontinuation or death, whichever is earlier.

8.6 Efficacy Subgroup Analyses

To evaluate of the impact of demographics and baseline characteristics on efficacy, subgroup analyses on efficacy endpoints including, but not limited to, RFS and OS will be performed for subgroups including, but not limited to, those defined below:

- Age $(< 60; \ge 60)$
- Gender (Male, Female)
- Previous treatment with venetoclax (Yes, No)
- Previous treatment with azacitidine (Yes, No)
- MRD prior to randomization ($\geq 10^{-3}$, $< 10^{-3}$, Unknown)
- Previous treatment with venetoclax or azacitidine (Yes, No)
- Previous treatment with venetoclax (Yes, No)
- Previous treatment with azacitidine (Yes, No)
- NCCN cytogenetic risk (Intermediate, Poor)
- Best response from conventional chemotherapy prior to randomization (CR, CRi)
- ECOG performance status (0, 1, 2)
- Molecular marker (
- Hepatic impairment (Yes, No)
- Renal impairment (Yes, No)

- Stratification factor: relapse risk (poor risk cytogenetic or MRD-positive $(\ge 10^{-3})$, others)
- Bone marrow blast count at diagnosis (< 30%, $\ge 30\%$ < 50%, $\ge 50\%$)
- region (Stratification regions (
), or other regions requested by regulatory agencies)
- CYP3A inhibitors use leading to venetoclax dose reduction (Yes, No)
- Post-study treatment (Yes, No)

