2.3 Treatment Assignment and Blinding

This study has two parts:

- Part 1 Dose Confirmation (see protocol V2.0 Section 4.1)
- Part 2 randomized, open label, 2-arm

In Part 2 of the study, subjects will be randomized 1:1 to one of the following two arms:

- Arm A: Receive combination of Venetoclax and AZA for up to the first 6 cycles and Venetoclax (monotherapy) from Cycle 7 to Cycle 24.
- Arm B: Receive best supportive care (BSC) only.

Randomization will be stratified by:

[figure not shown]

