4.0 Analysis Populations

The following population sets will be used for the analyses.

The Intent-to-Treat (ITT) Population includes all randomized subjects. The ITT Population will be used for all efficacy analyses. Subjects will be included in the analysis according to the study arm that they are randomized to.

[figure not shown]
The Safety Analysis Set consists of all subjects who received at least 1 dose of study drug (venetoclax and AZA) in Part 1 or Arm A in Part 2, and all randomized subjects in Arm B in Part 2. Arm A subjects in Part 2 who did not receive any dose of venetoclax and AZA will not be included in the Safety Analysis Set.

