8.3 Primary Efficacy Endpoint(s) and Analyses

8.3.1 Primary Efficacy Endpoint(s)

The primary efficacy endpoint is IRC-assessed relapse-free survival (RFS). RFS is defined as the time from randomization to death from any cause or disease relapse, whichever occurs first. Criteria for disease relapse are described in the IRC charter. All RFS events included in the analysis will be based on IRC adjudication. The primary analysis of RFS will occur when the is observed in the ITT population. All subjects in the ITT population will be included in the RFS analysis.

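### SAP 8.6 lists two factors that can arise after time zero, one of them possible only on venetoclax, among its baseline subgroups for RFS and OS

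*SAP*

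**What the plan says.** SAP 8.6 gives the purpose of its subgroups as assessing the "impact of demographics and baseline characteristics on efficacy", and states that "subgroup analyses on efficacy endpoints including, but not limited to, RFS and OS will be performed". Near the end of the list stand "CYP3A inhibitors use leading to venetoclax dose reduction (Yes, No" and "Post-study treatment (Yes, No". Neither comes with a time point, a landmark, a time-dependent method or a restriction to one arm.

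The surrounding rules are:

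- **Population.** SAP 4.0: "The ITT Population will be used for all efficacy analyses". That population is all randomized subjects in both arms.
- **Control arm.** SAP 2.3: "Arm B: Receive best supportive care (BSC) only".
- **Time origin.** SAP 8.3.1: "RFS is defined as the time from randomization to death from any cause or disease relapse". In the current Protocol 7.3, RFS and OS run from drug assignment.
- **How a reduction comes about.** Protocol 5.4 ties a venetoclax dose reduction (Protocol Table 4) to any co-administered strong or moderate CYP3A inhibitor. It also has subjects already on such an inhibitor before Cycle 1 Day 1 begin venetoclax at the reduced dose.

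The SAP was written for protocol Version 2.0. Protocol section 3 records that Part 2, the only part with a best-supportive-care arm, was removed in Version 5.0.

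**The concern.** A subgroup factor in a time-to-event comparison should be fixed at or before time zero and possible in every arm. The CYP3A item fails the second condition outright and may fail the first.

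If it is analysed as listed, one level yields no treatment comparison. The other compares Arm A subjects chosen partly by what happened to them during follow-up with an unselected control arm. Where the label is acquired during follow-up, the event-free wait before the inhibitor starts is credited to Yes, and subjects who relapse or die before any inhibitor is started fall into No. Reported as a baseline subgroup, the output could be read as a difference between kinds of patient when part of it comes from the labelling.

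Post-study treatment is likewise not known at time zero.

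**Working it through.** The SAP gives no figure on this point to reproduce. The first two steps set the provisions side by side; the third is an illustration.

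**1. Who can be Yes?** A subject must take venetoclax to have it reduced. Arm B takes none, so the Yes level holds Arm A subjects only, and No holds the rest of Arm A plus all of Arm B. This needs no assumption.

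**2. Can the label arise after time zero?** Yes, though not in every case. Subjects on an inhibitor before Cycle 1 Day 1 are Yes from the first dose. Later starts are foreseeable: entry requires an ANC of at least 1,500/µL (Protocol 5.1), while Protocol 6.2 recommends anti-infective prophylaxis, antifungal included, when ANC falls below 500/µL at any time, and points to Protocol Table 4 for interactions. The documents do not say how many users are of each kind.

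**3. How much does the mix matter?** Assumptions, none from the documents except the horizon: exponential RFS with median 15 months, no effect of the reduction, inhibitor start at a constant rate unrelated to prognosis, and 30% of subjects becoming users before an event and within the horizon. The horizon is τ = 22 months (24 cycles × 28 days = 672 days).

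- Event rate: λ = ln 2 / 15 = 0.04621 per month.
- All subjects, per head: events 1 − exp(−λτ) = 0.6382; person-months 0.6382 / 0.04621 = 13.81.
- b is the share on an inhibitor at baseline. The start rate μ among the rest solves (1 − b) · μ/(λ+μ) · [1 − exp(−(λ+μ)τ)] = later share.
- W is the person-months that later starters spend waiting: the integral over 0 to τ of s(1 − b)μ·exp(−(λ+μ)s).
- P is their person-months after starting: the integral of (1 − b)μ·exp(−(λ+μ)s)·[1 − exp(−λ(τ − s))]/λ.
- Yes events = λ(13.81b + P). Yes person-months = 13.81b + W + P. No is the remainder. W adds time to Yes but no events, and that is the whole bias.

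For b = 0 and 30% later, μ = 0.02757, W = 2.444 and P = 2.931. Yes rate = 0.04621 × 2.931 / 5.375 = 0.0252. No rate = (0.6382 − 0.1354) / (13.811 − 5.375) = 0.0596. Ratio = 0.42.

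| Baseline / later use | W | P | Yes rate | No rate | Yes/No | No / all Arm A |
|---|---|---|---|---|---|---|
| 0% / 30% | 2.444 | 2.931 | 0.0252 | 0.0596 | 0.423 | 1.29 |
| 10% / 20% | 1.691 | 1.918 | 0.0306 | 0.0551 | 0.555 | 1.19 |
| 20% / 10% | 0.879 | 0.939 | 0.0373 | 0.0506 | 0.738 | 1.10 |
| 25% / 5% | 0.449 | 0.464 | 0.0415 | 0.0484 | 0.857 | 1.05 |
| 30% / 0% | 0 | 0 | 0.0462 | 0.0462 | 1.000 | 1.00 |

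The true value is 1.00 throughout. Monte Carlo runs of the same model give 0.42, 0.56, 0.74 and 0.86 for the first four rows. The last column is the factor by which the No part of Arm A overstates the event rate of the whole arm, so the No comparison leans against venetoclax.

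**4. Do the alternatives remove the bias?** This was simulated with 300,000 subjects per arm, control median 8, 12 or 18 months, and an assumed Arm A hazard ratio of 0.65 because the planned value is redacted. With true hazard ratio 1.00 for reduced against full dose, a time-dependent covariate within Arm A returns 0.98 to 1.01, and a Cycle 1 Day 1 label 1.00 to 1.02. With true ratio 1.54 (1/0.65), they return 1.52 to 1.55 and 1.38 to 1.55; later starters dilute the baseline label.

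**5. Post-study treatment.** Either arm can have it, so the missing-comparator argument does not apply. By its name it follows study treatment, so it is not a baseline characteristic. Its size was not computed.

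**The case against.** The strongest reply is that no currently planned comparison is affected. Part 2 is gone, and the SAP's efficacy population is randomized subjects, of whom the current study has none. Protocol 7.3 plans Kaplan-Meier estimates of RFS and OS and names no subgroups; these are additional endpoints in Part 3, with 46 subjects enrolled. No provision carries the 8.6 list over to Part 3. This stands, and it sets the severity. What remains is that Protocol 7.1 has the SAP finalized before database lock and Protocol 7.3 defers further efficacy analyses to it, so the list will have to be kept, changed or dropped.

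Three stronger readings are tempting, and the documents do not support them:

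- **That every Yes subject had to stay event-free until an inhibitor was needed.** Protocol 5.4 makes baseline users Yes from the first dose. The SAP leaves timing undefined; it does not define the factor as on-treatment only.
- **That the subgroup is meant to show whether the interaction dosing preserves efficacy, and so gives false reassurance.** The SAP assigns it no such purpose, and it is outside the testing sequence in SAP Table 5. In the two-arm analysis Yes has no comparator, and No leans against venetoclax. A favourable Yes result appears only if Yes is contrasted with No among treated subjects, which 8.6 does not specify.
- **That the bias in this trial is as large as 0.34 to 0.43.** That range (medians 10 to 20 months, 30 to 50% users) assumes no baseline use at all.

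The direction is also conditional. If inhibitors are started because of infection or neutropenia, users may differ in prognosis, and the net bias could be smaller or different.

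**Conclusion.** The point holds as a minor one. Two factors that need not be baseline characteristics are listed as such, and one of them cannot occur in the control arm. The absent comparator at the Yes level and the selected Arm A subset at the No level follow directly from the SAP's text.

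The time bias depends on the share of use that starts late. Under the stated assumptions the Yes/No ratio runs from 0.42 with all use later to 1.00 with all use at Cycle 1 Day 1. These figures show direction and range; they do not predict this trial's results. The SAP's primary RFS analysis and testing sequence are untouched. With Part 2 removed, the defect matters only when the SAP is brought into line with the current protocol.

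**What to change.** When the SAP is updated, remove both items from the baseline subgroup list in 8.6.

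If the CYP3A question is wanted, state it separately as exploratory and restrict it to venetoclax-treated subjects. Define exposure either as strong or moderate inhibitor use at Cycle 1 Day 1, or as a time-dependent covariate that switches when the inhibitor starts.

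The cost is SAP wording and minor programming, since Protocol 5.4 already requires start and end dates for concomitant medication. The downsides are a smaller subgroup under the baseline definition and, under either definition, a non-randomized contrast that remains open to confounding by infection or neutropenia. The write-up should say so.

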9.0 Safety Analyses

[figure not shown]
9.1 General Considerations

Safety analyses will only include subjects in the Safety Analysis Set as defined in Section 4.0. Safety summaries will be presented for Part 1 and Part 2 separately and will present for overall, for each study arm in Part 2, and for each dose level in Part 1. Unless otherwise specified, data after the cutoff date will be excluded from statistical analyses.

Adverse events (AEs) will be summarized and presented using primary MedDRA System Organ Classes (SOCs) and preferred terms (PTs) according to the version of the MedDRA coding dictionary used for the study at the time of database lock. The actual version of the MedDRA coding dictionary used will be noted in the AE tables and in the clinical study report. Specific adverse events will be counted once for each subject for calculating percentages, unless stated otherwise. In addition, if the same adverse event occurs multiple times within a subject, the highest severity and level of relationship to investigational product will be reported.

9.2 Treatment-Emergent Adverse Events

Treatment-emergent AEs are defined as any AE with the onset that is on or after the first dose of study drug until 30 days after the last dose of the study drug for subjects in Part 1 and ARM A of Part 2. If an incomplete or missing onset date was collected for an AE, the AE will be assumed to be treatment-emergent unless there is evidence that confirms that

[figure not shown]
the AE was not treatment-emergent (e.g., the AE end date was prior to the date of the first dose of study drug). For subjects randomized to Arm B, AEs with an onset date on or after the date of randomization up to 30 days after the end of Cycle 24, disease relapse or study discontinuation, whichever is the earliest will be included in the summaries of treatment-emergent AEs.

All treatment-emergent AEs will be summarized overall, for venetocalx combination with azacitidine as well as for venetoclax monotherapy separately.

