See Appendix D and Table 7 and Table 8 for dose interruptions and reductions for toxicities related to venetoclax + AZA or oral AZA and Table 6 for recommendations for reinitiating venetoclax treatment after interruption.

If ANC drops below $500/\mu L$, venetoclax may be interrupted for ANC recovery until ANC $\geq 500/\mu L$ or up until 14 days. For subjects who have not recovered (ANC $\geq 500/\mu L$) within or beyond 14 days of interruption, per investigator discretion, a bone marrow sample may be collected and analyzed to exclude relapse before proceeding. If relapse is confirmed, subjects should be withdrawn from the study treatment for alternative therapy. If relapse is excluded, per investigator discretion, growth factor support may be used to stimulate count recovery. If a subject presents with new onset Grade 4 neutropenia for more than 1 week during subsequent cycles, unless it is thought to be due to the underlying disease, venetoclax dosing may be interrupted until ANC recovery ($\geq 500/\mu L$) per investigator discretion and in consultation with the AbbVie TA MD. Venetoclax may be reinitiated at a lower dose based on Table 6. For subjects who require interruption or delay of study drug administration for cytopenia, venetoclax may be administered for 21 days out of 28 days during each of the subsequent cycles. If a subject continues to have persistent cytopenia (i.e., ANC < 1,000/ μL) and/or platelets < 50,000/ μL) venetoclax may be administered for 14 days out of 28 days during each of the subsequent cycles. Subjects who develop cytopenias during subsequent cycles will have reduction in the duration of

venetoclax dosing as described in Table 6 beginning from whichever cycle cytopenias were first observed.

Venetoclax dose modifications for possible drug-drug interactions are provided in the Section 5.4.

Table 6. Reduced Duration of the Venetoclax Dosing Schedule for Subjects (Part 1 Only)

| Reduced Duration of Venetoclax ^a | Absolute Neutrophils/Platelets | Venetoclax Dosing Schema |
|--|-----------------------------------|--|
| First reduction | < 500/μL/< 25,000/μL | Venetoclax 400 mg Days 1 through 21 for each 28-day cycle |
| Second reduction | < 1,000/μL/< 50,000/μL | Venetoclax 400 mg Days 1 through 14 for each 28-day cycle |
| Subsequent reduction | < 1,000/μL/< 50,000/μL | Venetoclax 400 mg Days 1 through 10 for each 28-day cycle |

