9.3 Analysis of Laboratory Data

Unless otherwise specified, analysis of laboratory data will include post-baseline measurements within 30 days of the last dose of the study drug for Arm A or Part 1 or within 30 days of the end of Cycle 24, disease relapse, or study discontinuation whichever is the earliest for subjects in Arm B.

Data collected from central and local laboratories, including additional laboratory testing due to an SAE, will be used in all analyses. The clinical laboratory tests defined in the protocol operations manual (e.g., hematology and clinical chemistry) will be summarized. Change from baseline will be summarized and presented for each lab test at scheduled post-baseline visits defined in Appendix C. Baseline is defined as the last non-missing observation before the first administration of study drug or randomization if no study drug is given.

For shifts relative to National Cancer Institute Common Toxicity Criteria for Adverse Events (NCI CTCAE version 4.03), baseline and post-baseline laboratory observations will be categorized as grade 0, grade 1, grade 2, grade 3, or grade 4 according to NCI CTCAE grade version 4.03. The baseline grade is defined as the grade of the last measurement collected on or prior to the first dose of study drug (or randomization for non-treated subjects). In cases where multiple values are collected on the same day, the maximum grade value will be selected as the value for that day. The maximum NCI toxicity grade value is the value with highest NCI toxicity grade collected after the first dose of study drug.

For each lab test, cross tabulate will be generated for the number of subjects with baseline values of grade 0, grade 1, grade 2, grade 3, grade 4, or missing grade versus maximum post-baseline values of grade 0, grade 1, grade 2, grade 3, grade 4, or missing grade. All subjects in the safety analysis set will be included in the cross tabulation regardless whether baseline or post-baseline measurements are collected.

The separate laboratory shifts tables based on the two criteria below will be generated for each laboratory tests related to CTCAE:

- 1. Shifts from grade 0 (normal) at baseline to grade 1 4 post-baseline (maximum) and worsening from an abnormal baseline value of at least one grade up post-baseline (maximum)
- 2. Shifts from grade 0 2 at baseline to grade 3 or 4 post-baseline (maximum) and from grade 3 at baseline value to grade 4 post-baseline (maximum).

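### The safety plan has no analysis that separates events after the start of subsequent AML therapy, so Part 1 all-cause Grade ≥3 AE tables and maximum-grade laboratory shift tables can include toxicity of a post-relapse regimen

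*SAP*

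**What the plan says.** **AE window.** SAP 9.2 takes onsets from first dose "until 30 days after the last dose of the study drug for subjects in Part 1", and likewise for Arm A of Part 2. For the former control arm the window runs "up to 30 days after the end of Cycle 24, disease relapse or study discontinuation, whichever is the earliest". SAP 9.1 excludes only data after the cutoff date.

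**Laboratory window.** Under SAP 9.3, "analysis of laboratory data will include post-baseline measurements within 30 days of the last dose of the study drug for Arm A or Part 1". The worst value is defined without reference to other therapy: "The maximum NCI toxicity grade value is the value with highest NCI toxicity grade collected after the first dose of study drug". All sources count: "Data collected from central and local laboratories, including additional laboratory testing due to an SAE, will be used in all analyses".

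**Collection.** Protocol 3.4 and 6.1 both run safety evaluation and AE collection to 30 days after study drug ends, so the SAP window agrees with them. Protocol Appendix H schedules AE assessment, chemistry, hematology and prior/concomitant therapy at the 30-day visit in Parts 1 and 3.

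**Relapse and new therapy.** Protocol 5.5 lists relapse as a reason to stop study treatment. Protocol 6.2 says, for subjects in the cytopenia work-up, "If relapse is confirmed, subjects should be withdrawn from the study treatment for alternative therapy". The SAP's one analysis rule that acts on other AML therapy is an RFS sensitivity analysis (SAP 8.3.4): "Modified primary RFS definition with censoring subjects who received other non-protocol treatment for AML prior to relapse".

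**The concern.** Myelosuppression and its complications are the toxicities that the plan watches most closely. SAP 9.2.4 selects Grade ≥3 neutropenia and infection, haemorrhage, anaemia, thrombocytopenia and leukopenia. A cytotoxic regimen given after relapse could produce the same events. If such a regimen starts within 30 days of the last dose, its toxicity falls inside the treatment-emergent window, and nothing in the planned output lets a reader see this.

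Three other SAP rules add to the effect:

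- Repeated AEs are reported at their highest severity (SAP 9.1 and 9.2.2), so a later, worse episode replaces the on-drug grade.
- Medication started after the last dose is not a concomitant medication (SAP 7.3). The toxicity would be tabulated while the therapy behind it is absent from that table.
- Treatment-emergent AEs are also summarized separately for venetoclax monotherapy (SAP 9.2). A relapse after azacitidine has ended could place another regimen's toxicity there.

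What is at stake is the descriptive Part 1 safety profile, including its comparison across dose levels. Extra counts of this kind follow relapse and the timing of the next treatment, not the toxicity of the dose level under which they appear.

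**Working it through.** The plan states no figure on this point, so there is none to reproduce. The check has two parts.

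**1. Is there a rule anywhere?**

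| Place | Upper limit | Rule for subsequent AML therapy |
|---|---|---|
| SAP 9.1 | data cutoff | none |
| SAP 9.2, Part 1 | 30 days after last dose | none |
| SAP 9.3, Part 1 | 30 days after last dose | none |
| SAP 9.3, maximum grade | highest value after first dose, within the section's 30-day limit | none |
| Protocol 3.4 and 6.1 | 30 days after last dose | none |
| Protocol 7.4 | treatment-emergent not defined | none |
| SAP 8.3.4 (efficacy) | not applicable | censoring, in a sensitivity analysis only |

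Protocol 5.3 bars cytotoxic agents while a subject is in the study. That does not close the gap: relapse ends study treatment, and Appendix H records post-treatment cancer therapies in Part 3 survival follow-up. The Operations Manual is not in the supplied text, so a rule there cannot be excluded.

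**2. What does one affected subject weigh?**

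Inputs: 66 subjects enrolled in Part 1, and cohorts of about 20 (Protocol 4.1).

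- Weight of one subject = 100/n percentage points.
- n = 66: 100/66 = 1.5 points.
- n = 20: 100/20 = 5 points.

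The number affected cannot be taken from the documents. For scale only, let

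expected number = 66 × a × b × c × d,

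with each factor conditional on the ones before it. All four are assumptions:

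| Factor | Low | Middle | High |
|---|---|---|---|
| a: relapse on treatment | 0.20 | 0.30 | 0.50 |
| b: new therapy within 30 days of last dose | 0.25 | 0.50 | 0.75 |
| c: no earlier Grade ≥3 cytopenia | 0.20 | 0.40 | 0.60 |
| d: Grade ≥3 cytopenia captured in the window | 0.50 | 0.90 | 0.90 |
| a × b × c × d | 0.005 | 0.054 | 0.2025 |
| Subjects of 66 | 0.3 | 3.6 | 13.4 |
| Percentage points | 0.5 | 5.4 | 20 |

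The range is wide because nothing in the documents narrows it. It concerns Grade ≥3 rates. A subject already at Grade 3 on drug who reaches Grade 4 on the next regimen leaves those rates unchanged but still moves a cell in the baseline-to-maximum cross-tabulation.

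**The case against.** **The window is the protocol's own.** It matches Protocol 3.4 and 6.1, and an all-cause 30-day window is an accepted, conservative convention. A reader might infer that it is wrong and that the main tables should be cut at new therapy. The documents do not support that. Such a cut would depart from the protocol's safety definition and move late study-drug effects out of the main table. This objection stands, and it decides the form of the fix.

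**The relapse text is weaker than it looks.** The Protocol 6.2 sentence concerns subjects whose ANC has fallen below 500/µL and not recovered after an interruption. They already have Grade 4 neutropenia on drug, so later therapy cannot raise their maximum neutrophil grade. It could still add thrombocytopenia, anaemia, haemorrhage or infection. Protocol 5.5 covers relapse more generally but does not say when new therapy begins.

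**The RFS parallel is limited.** SAP 8.3.4 concerns therapy before relapse and is only a sensitivity analysis. By analogy it supports a supplementary safety summary and nothing stronger.

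**Few scheduled values fall in the window.** The Final Visit is within 2 weeks of the last dose, and the 30-day visit has a ±3-day allowance, so it may fall just outside. This stands for scheduled samples, but local and SAE-driven tests are also used.

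**Part of the output is protected.** SAP 9.2.1 has separate rows for events related to venetoclax and to azacitidine, and a laboratory abnormality becomes an AE only under the criteria in Protocol 6.1. The all-cause AE tables and the shift tables have no such filter.

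**Conclusion.** The gap is real and modest in reach. No supplied text ends the safety windows at subsequent AML therapy, and no planned analysis separates the events that follow it. The outputs affected are the Part 1 all-cause AE tables (Grade ≥3, serious and selected events) and the maximum-grade laboratory shift tables, overall and by dose level. The weight is about 1.5 points per affected subject in 66, or 5 points in 20. How many subjects are affected is unknown.

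Three stronger readings are tempting and are not supported:

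- *The recommended dose is compromised.* It rests on Cycle 1 dose-limiting toxicities considered related to venetoclax (Protocol 4.1 and 6.3), which this barely touches.
- *Grade 3–4 rates are substantially overstated, most at dose levels with more relapses.* The documents give neither relapse rates by dose level nor the share of subjects starting new therapy within 30 days. The protocol's remark that most patients relapse concerns patients who reach remission with induction, not relapse during maintenance treatment.
- *The comparison with the control arm is biased.* Part 2 was removed from the protocol, so the SAP's control-arm window has no practical effect.

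The SAP is written for protocol version 2.0 and does not cover Part 3. Protocol 7.4 leaves treatment-emergent undefined there, so the question is open for Part 3.

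**What to change.** Keep the 30-day window for the main AE and laboratory tables. Add to SAP 9.2 and 9.3:

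1. A supplementary summary of Grade ≥3 treatment-emergent AEs, the selected cytopenia and infection events, and the laboratory shift tables. Cut it at the earlier of 30 days after last dose and the day before first subsequent AML therapy, and present it by dose level.
2. A listing of the AEs and laboratory values that fall between the two cut-offs, with the start date of the new therapy.
3. The same rule in the SAP update that Part 3 needs, together with a definition of treatment-emergent for that part.

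The therapy start date can be derived from the therapy records collected through the 30-day visit in both parts. Protocol 7.1 has the SAP finalized before database lock, which is the point by which to add this. Data collection and expedited reporting do not change.

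The cost is one derived date and a few extra tables. The small downside is that a late study-drug effect first seen after new therapy starts is absent from the supplementary summary, though it remains in the main table and appears in the listing.
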